**Research on the Construction of a Prognostic Model for COPD
Complicated with Sarcopenic Obesity Based on Bioelectrical
Impedance Phase Angle Technology (COSAT)**

Research Protocol

Main researchers: [name], [name]

Clinical research department: Respiratory and Critical Care

Medicine Sponsor: [name]

Ethics Review No.:2025K200

Scheme Version No: 01

Plan Preparation date: July 15th, 2025

Research Objectives:

This study aims to explore the diagnosis, impact, and prognostic factors of COPD complicated with sarcopenic obesity using multi-segment bioelectrical impedance phase angle technology. It seeks to clarify the diagnostic value and efficacy of body composition analysis in specific populations, analyze the relationship between phase angle and COPD severity as well as quality of life, investigate its predictive role for adverse outcomes, and reveal the effects of inflammation and metabolic disorders in sarcopenic obesity. The goal is to provide a basis for early screening and precise intervention to improve patient prognosis.

Proposed Research Methods

Inclusion Criteria

- (1) Age over 65 years;**
- (2) Ability to complete physical activity assessments and pulmonary function tests;**
- (3) Complete medical records, willingness to adhere to follow-up arrangements, and provision of adverse event reports via telephone or outpatient visits, with signed informed consent;**
- (4) COPD diagnosis based on the American Thoracic Society (ATS)/European Respiratory Society (ERS) GOLD definition, with a post-bronchodilator FEV1/FVC ratio < 0.70, current or former smokers with a smoking history of ≥ 10 pack-years.**

Exclusion Criteria:

- (1) Severe cognitive impairment or hand deformities (e.g., rheumatoid arthritis) preventing body composition measurements;**
- (2) Incomplete clinical or follow-up data or unwillingness/inability to undergo regular follow-up;**
- (3) Severe systemic edema;**
- (4) Presence of cardiac pacemakers or significant metal implants that may interfere with measurements;**
- (5) Voluntary withdrawal for any reason, including loss to follow-up.**

Data Collection:

Demographic and clinical data: Gender, smoking status (never, former, current), age, height, weight, waist circumference, BMI, skeletal muscle index (SMI), body fat content,

visceral fat index, and segmental phase angles measured via bioelectrical impedance analysis.

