Clinical records: Smoking history, comorbidities (Charlson Comorbidity Index), nutritional status (MNA-SF), physical performance (SPPB), medication use, pulmonary function tests, COPD exacerbations in the past year, CAT score, mMRC score, and St. George's Respiratory Questionnaire (SGRQ).

Laboratory tests: Blood samples for CBC, CRP, cholesterol, albumin, HbA1c, IL-6, and TNF- α (ELISA).

Sample Size Calculation:

Using PASS 15.0 for repeated-measures ANOVA ($\alpha = 0.05$, power = 90%), with a COPD prevalence of 15% and a 2:1 ratio for sarcopenic obesity vs. non-sarcopenic groups, the study requires 200 participants (33 sarcopenic obese, 33 non-obese sarcopenic, 72 obese non-sarcopenic, and 72 non-obese non-sarcopenic).

Diagnostic Criteria:

Sarcopenia: Asian Working Group criteria: SMI (InBody S10) $<7.0 \text{ kg/m}^2$ (men) or $<5.7 \text{ kg/m}^2$ (women); grip strength $<28 \text{ kg}$ (men) or $<18 \text{ kg}$ (women); gait speed $<0.8 \text{ m/s}$. **Obesity:** BMI $\geq 28 \text{ kg/m}^2$ or waist circumference $\geq 85 \text{ cm}$ (men)/ $\geq 80 \text{ cm}$ (women); body fat $\geq 24.3\%$ (men) or $\geq 33.2\%$ (women).

sarcopenic Obesity: Coexistence of sarcopenia and obesity.

Assessments:

Physical Performance: Short Physical Performance Battery (SPPB: balance, gait speed, chair stands; score 0–12).

Nutritional Status: Mini Nutritional Assessment (MNA-SF; score 0–12).

Phase Angle: Measured via InBody S10 at six frequencies (1kHz–1000kHz) across five body segments, calculated using resistance (R) and reactance (Xc):

$\text{PHA} = \arctan((\text{Xc_right arm} + \text{Xc_trunk} + \text{Xc_right leg}) / (\text{R_right arm} + \text{R_trunk} + \text{R_right leg})) \times 180^\circ / \pi$.

Follow-up Endpoints:

Primary: Changes in pulmonary function, dyspnea scores, and body composition at 2 years.

Secondary: Acute exacerbations, hospitalizations, or death within 2 years. Follow-ups at 6, 12, and 24 months.

Grouping patients based on whether they have sarcopenic obesity, the differences in clinical data between the two groups were analyzed. Statistical analysis was performed using SPSS 24.0 statistical software.

Analysis of Demographic Characteristics and Clinical Data:

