The age and gender distribution of the patients were described. Based on whether the patients had sarcopenic obesity, they were divided into two groups. The differences in clinical data between the two groups, including age distribution, smoking status, obesity-related body fat, pulmonary function, whole-body and segmental phase angle, were analyzed. Continuous variables were expressed as mean \pm standard deviation, and categorical variables were expressed as percentages. Differences between groups were analyzed using Student's t-test for continuous variables and the chi-square test for categorical variables, depending on the data type.

Analysis of Factors Associated with COPD Complicated by Sarcopenic Obesity:

Univariate and multivariate analyses were conducted on data from COPD patients with sarcopenic obesity. Using clinical data variables, nutritional status, physical activity capacity, whole-body and segmental phase angle, logistic regression was applied to analyze the factors associated with sarcopenic obesity in COPD patients.

Analysis of the Prognostic Predictive Value of Sarcopenic Obesity in Obstructive Pulmonary Disease:

The differences in hospital stay length, acute exacerbation readmission rate, and mortality between COPD patients with sarcopenic obesity and those without sarcopenia at baseline were compared. Kaplan-Meier analysis was used for statistical analysis, and differences were expressed using the log-rank test.

COSAT study

INFORMED CONSENT FORM

This document provides you with information to help you decide whether to participate in this clinical research study. Please read it carefully. If you have any questions, please direct them to the researcher in charge of this study.

Your participation in this study is voluntary. This research has been reviewed and approved by the institutional ethics review committee of our research institution.

The background, objectives, research process, and other important information are as follows:

Research Purpose:

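### Kaplan-Meier is the only method named for readmission, stay length and mortality, with no rule for deaths; a readmission rate read from it would be too high, and stay length would be ambiguous

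*Combined protocol and SAP*

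**What the plan says.** The section on the prognostic predictive value of sarcopenic obesity lists its outcomes separately: "The differences in hospital stay length, acute exacerbation readmission rate, and mortality between COPD patients with sarcopenic obesity". The comparator is patients free of sarcopenia at the start. The next sentence gives the only method in that section: "Kaplan-Meier analysis was used for statistical analysis, and differences were expressed using the log-rank test".

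Under Follow-up Endpoints, the plan has "Secondary: Acute exacerbations, hospitalizations, or death within 2 years", with the schedule "Follow-ups at 6, 12, and 24 months". The first inclusion criterion is "Age over 65 years", and all participants have COPD.

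The documents do not say whether a patient who dies before any readmission is censored or counted as an event. Nor do they say how an in-hospital death enters the stay-length analysis. They mention no cumulative incidence, cause-specific or other competing-risk method.

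**The concern.** Death rules out any later readmission and ends a hospital stay without a discharge. In older patients with COPD followed for 2 years, with death a declared endpoint, the plan itself expects deaths. A Kaplan-Meier curve for readmission that censors deaths treats those patients as still open to readmission, so its complement is not the proportion readmitted.

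The study asks whether sarcopenic obesity worsens prognosis. If it raises mortality, the same death-handling choice inflates the readmission figure in that group and, under one coding, shortens its apparent stays. Readmission, stay length and mortality could then give conflicting messages partly because of how deaths were coded.

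**Working it through.** **What can be reproduced.** The documents give no readmission, mortality or stay-length figure, so there is no plan figure to reproduce here. All rates below are assumptions, shown as ranges.

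**Readmission: direction.** Take constant hazards over the 2 years, with a the cumulative readmission hazard and b the cumulative hazard of death before readmission.

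- 1 minus Kaplan-Meier, deaths censored: 1 - exp(-a)
- Cumulative incidence (CIF): a/(a+b) × [1 - exp(-(a+b))]

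The second is smaller whenever b > 0, so the direction does not depend on the assumed rates.

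**Readmission: size.** Set a = -ln(1 - KM readmission) and b = -ln(1 - 2-year death risk).

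Worked case, KM 40% and death 25%: a = 0.511, b = 0.288, and 1 - exp(-(a+b)) = 1 - 0.60 × 0.75 = 0.55. CIF = 0.511/0.799 × 0.55 = 35.2%.

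| KM readmission | 2-year death risk | CIF | Overstatement (points) |
|---|---|---|---|
| 30% | 10% | 28.6% | 1.4 |
| 30% | 30% | 25.5% | 4.5 |
| 40% | 10% | 38.1% | 1.9 |
| 40% | 25% | 35.2% | 4.8 |
| 50% | 10% | 47.7% | 2.3 |
| 50% | 30% | 42.9% | 7.1 |

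At a fixed readmission hazard the overstatement grows with mortality.

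**Effect on a group difference.** Suppose one group has KM readmission 60% with 30% mortality, and the other 50% with 10%. The KM difference is 10 points. The cumulative incidences are 51.8% and 47.7%, a difference of 4.1 points.

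**Where the pattern reverses.** KM 10% with 30% mortality gives CIF 8.4%, an overstatement of 1.6 points. KM 60% with 15% mortality gives CIF 56.1%, an overstatement of 3.9 points. The group with more deaths therefore has the larger absolute overstatement only when readmission hazards are similar.

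**Stay length.** Assume a discharge hazard c = 0.10 per day in every scenario and an in-hospital death hazard d of 0.005, 0.01 or 0.02 per day. The share dying in hospital is d/(c+d).

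- Death coded as end of stay: median = ln 2/(c+d)
- Death censored: median = ln 2/c
- Day by which half of all admissions are discharged alive: -ln(1 - 0.5(c+d)/c)/(c+d)

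| In-hospital death | Median, death ends stay | KM median, death censored | Half discharged alive |
|---|---|---|---|
| 4.8% | 6.6 days | 6.9 days | 7.1 days |
| 9.1% | 6.3 days | 6.9 days | 7.3 days |
| 16.7% | 5.8 days | 6.9 days | 7.6 days |

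The discharge hazard is the same in every row. With death as end of stay, more deaths look like shorter stays. With death censored, the deaths leave no trace. In fact live discharge takes longer to reach half the admissions as deaths increase.

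**The case against.** The best defence has four parts.

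- **The plan does not say that deaths are censored.** This is correct. Censoring is the usual coding, not a stated rule. The gap is the lack of any rule for death together with the lack of a competing-risk method.
- **The log-rank test is sound.** This also stands. With deaths censored it validly compares cause-specific readmission hazards. A reader might infer that Kaplan-Meier and log-rank fit mortality alone and that the readmission test is invalid; that does not follow. The bias lies in reading 1 minus Kaplan-Meier as a readmission rate. The plan does not say outright that it will read the rate that way, but a readmission rate is what it sets out to compare and Kaplan-Meier is the only estimator it names.
- **The method sentence is not tied to each outcome.** The t-test and chi-square test appear in the section on demographic and clinical data, and whether they extend to stay length is unclear. The stay-length part therefore rests on taking the prognostic section as written, where no other method is named.
- **The endpoint could be a composite.** The wording "Acute exacerbations, hospitalizations, or death within 2 years" allows that reading. Nothing confirms it, and the analysis section lists readmission and mortality separately.

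**Conclusion.** The point holds for estimation. Following the stated method with the usual censoring gives a readmission rate that is too high whenever deaths occur before readmission: by 1.4 to 7.1 points for KM readmission of 30-50% and 2-year mortality of 10-30%, assuming constant hazards. For stay length, neither coding of an in-hospital death describes what happened to patients, and the plan does not choose between them. Mortality is unaffected. These are secondary endpoints, and the true size cannot be fixed from the documents.

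A reader might infer two further things that are not supported. One is that the rate is always overstated most in the group that dies more; the reversal shown above rules that out as a general statement. The other is that readmission-or-death should replace the readmission comparison because it may detect more. It tests a different hypothesis, since a difference in deaths alone can drive it, so a higher rejection rate would not show a fault in the readmission test.

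**What to change.** - **Mortality:** keep Kaplan-Meier with log-rank.
- **Readmission:** define the time origin, and state that a death before readmission is a competing event. Report the 2-year readmission rate per group as a cumulative incidence. Label the log-rank result, with deaths censored, as a comparison of cause-specific hazards. Time to readmission or death may be added as a supporting analysis.
- **Stay length:** if it is analysed as time to event, use time to live discharge with in-hospital death as a competing event, and report the number of in-hospital deaths per group alongside.

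Replacing stay length by days alive and out of hospital is not proposed. That is a different endpoint, and it may need dates of every admission, which the plan does not say it collects.

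**Cost:** a few sentences, best settled before outcome data are seen. The dates needed are those that Kaplan-Meier analyses of readmission, stay and death already require. Reported readmission rates will be slightly lower, and the cumulative incidence may need software other than SPSS 24.0.
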